We conducted a pilot randomized controlled trial (RCT) of an intervention providing five months of medically tailored meals (tapering down the amount of food each month), paired with nutrition education, to patients upon discharge from a safety-net hospital due to congestive heart failure (CHF) exacerbation. Participants were randomized to the intervention (n=106) versus control (n=86) using a parallel design. The goal was to test for feasibility and determine the preliminary impact of the intervention on heart-failure quality-of-life (primary outcome), and on in hospital readmission and emergency department visits (secondary outcomes). We also set out to determine the impact of this intervention on intermediate outcomes important to the health of our population (food security, diet, mental health and medication adherence), which may be on the path from the intervention towards improved heart failure health outcomes. The control arm continued with usual care during the study period and then received the five-month meal program starting the sixth month after discharge from the hospital. Participants were followed with full surveys at baseline, 1 month and 5 months; brief versions of the survey were administered at 2- and 3-months. In addition, we collected medical record data on healthcare utilization outcomes. Alongside the trial, a qualitative study and process evaluation was conducted, which included in-depth interviews with study participants and survey items added to the end-line survey to translate lessons learned to guide a possible scale-up of the intervention.

6) Randomization

Initially, 148 participants were randomized in a 1:1 allocation to the intervention (n=75) and control arms (n=73), stratified by food security (zero affirmative answers vs. at least one affirmative answers on the USDA 12-question food security screener) and healthcare utilization (<3 vs. >=3 hospital admissions at ZSFGH), based on a computer-generated assignment. However, early withdrawals were observed, which was higher in the intervention (n=27) than in the control arm (n=3). Therefore, the randomization of the last 44 participants were allocated in a 2:1 ratio for intervention (n=31) relative to control (n=13) arms to compensate for early withdrawals and have the final study arms balanced.

7) Sample size

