- b. Unable to be contacted: 16 intervention participants were randomized but were not able to be contacted by POH to start the intervention and were considered as early withdrawals. Control participants could not be excluded as "early withdrawals" because the next visit would be a month after the baseline. Therefore, researchers modified the protocol and made a phone call to the control participants, right after the randomization, to simulate the call that the intervention participants had by POH to be enrolled in the food and nutrition program. From among control participants called right after randomization in the modified protocol, 2 could not be reached and were considered early withdrawals.

The number of participants with major and minor protocol deviations will be summarized by study arm.

16) Analysis populations – definition of analysis populations, e.g. intention to treat, per protocol, complete case, safety

- a. Intent to treat - The primary analysis will be intent to treat (ITT). The ITT analysis will include all participants in both arms who were randomized, completed all baseline assessments, and who had at least one follow-up visit. (see CONSORT).
- b. Adjusted intention to treat analysis. To adjust for early withdrawals, a propensity score for receiving the intervention will be developed and used to estimate the probability of each participant to receive the intervention. The adjusted ITT analysis will be performed adjusting for the propensity score and for baseline covariates that were different between arms.
- c. Per protocol - The per protocol analysis will include all participants in the ITT sample with baseline and follow-up evaluations and who adhered to the food and nutrition intervention. The minimal adherence will be considered as receiving at least 50% of weeks food and groceries, and at least 1 visit with the dietitian. This definition may be

revised depending on the distribution of adherence in the intervention participants. See appendix 1 for details about the food and nutrition education intervention.

- d. Complete case— We will not conduct complete case analyses as we will attempt to use all available data from all participants.

Section 5: Trial Population

17) Screening Data –

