- a. **Preliminary/Descriptive analyses.** Frequency tables for all variables and measures of central tendency and variability for continuous variables will characterize the sample and be stratified by randomization arm to check for non-equivalence. If the two arms differ at baseline on any covariates, propensity scores approach will be used to obtain the desired marginal effect estimates under the counterfactual assumption of balanced arm.

25) Analysis methods to be used and how the treatment effects will be presented:

- a. Aim 1, Hypothesis 1. The intervention will lead to improved heart failure quality-of-life (primary outcome) and reduced acute care utilization (secondary outcomes) in the intervention arm compared to the control arm. Intent-to-treat analyses will assess whether the intervention will result in improved changes in primary and secondary outcomes with mixed effects models. These mixed models are equivalent to repeated measures models. Study arm (intervention or control), visits (baseline, month 1 and month 5), and the interactions between arms and visits will be the fixed effects and individuals will be considered as random effects.

Alternative analyses will be done using analysis of covariance in which the 5 month (and 1 month) outcome measures will be regressed on the corresponding baseline outcome measures and study arm. Analysis of covariance allows relaxing the assumption that the

baseline and follow-up measures have a 1:1 relationship and testing the assumption that the relationship between the baseline and follow-up measures are the same.

Additional analyses will be done to check robustness if the two arms differ at baseline by controlling for the propensity score or the covariates that were important in the propensity score.

For primary and secondary outcomes, Box-Cox transformations will be used to correct for skewness if needed.

To compare the probabilities of hospitalization and emergency room visits by study arm, a log-rank test will be performed, and visualized using Kaplan-Meier curves.

- b. Aim 2, Hypothesis, The intervention will improve food security, reduce healthcare utilization, and improve dietary behavior, that in turn will improve mental health (depressive symptoms), and medication adherence. Analysis for intermediate outcomes will be performed using mixed effects models, as described in Aim 1.
- c. Any planned sensitivity analyses for each outcome, where applicable: Not applicable.

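### The allocation ratio changed from 1:1 to 2:1 for the last 44 participants, but neither the primary mixed model nor the ANCOVA includes randomisation phase

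*Combined protocol and SAP*

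**What the plan says.** **Allocation (Section 3, item 6).** The first 148 participants were randomised 1:1, giving 75 intervention and 73 control. The plan then states that "early withdrawals were observed, which was higher in the intervention (n=27) than in the control arm (n=3"), and that in response "the randomization of the last 44 participants were allocated in a 2:1 ratio for intervention (n=31) relative to control (n=13) arms". The totals are 106 and 86.

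**Analysis set (Section 4, item 16a).** The primary ITT set is limited to participants "who were randomized, completed all baseline assessments, and who had at least one follow-up visit". Section 5, item 20 starts follow-up from 79 intervention and 82 control participants after early withdrawals. It reports 75 and 78 retained at month 1, and 60 and 59 at month 5.

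**Models (Section 6, item 25a, and item 22b).**
- Mixed model: "Study arm (intervention or control), visits (baseline, month 1 and month 5), and the interactions between arms and visits will be the fixed effects", with individuals as random effects.
- Alternative ANCOVA: the follow-up "outcome measures will be regressed on the corresponding baseline outcome measures and study arm".
- Admission and emergency department counts: adjusted for the value in the three months before baseline.
- Time to hospitalisation or emergency visit: "a log-rank test will be performed, and visualized using Kaplan-Meier curves". No strata are named.

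**Propensity analyses.** Item 16b says "The adjusted ITT analysis will be performed adjusting for the propensity score and for baseline covariates that were different between arms". Item 23a says that, if the arms differ at baseline, a "propensity scores approach will be used to obtain the desired marginal effect estimates under the counterfactual assumption of balanced arm". Neither lists the variables in the score, and neither is the primary analysis. Planned sensitivity analyses are marked as not applicable.

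**The concern.** The probability of receiving the intervention was 1/2 in the first phase and 2/3 in the second. Comparing the arms without regard to phase is then not a comparison of like with like: late enrollees are over-represented in the intervention arm by design, and the imbalance would recur in expectation if the trial were repeated. If KCCQ change over one or five months differed between early and late enrollees for any reason, part of that difference would be reported as an effect of the meals. The same applies to the admission counts, the emergency visit counts and the log-rank test.

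The documents record several changes during the trial: a new post-randomisation call to controls and a revised retention procedure (Section 4, item 15), and dietitian visits by phone during COVID-19 (Appendix 1, Table A1.1). None is dated or tied to the switch in ratio. They show that conditions were not constant. They do not show that KCCQ change differed by phase.

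**Working it through.** **1. The plan's own figure.** Section 3, item 7 uses a 10-point difference, SD 20, two-sided alpha 0.05 and 80% power. The two-sample formula gives 63 per arm, and 63/0.80 rounds up to 79 per arm, 158 in total. Both match the plan, so SD 20 and the 10-point difference are used below.

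**2. Imbalance in phase.**
- All randomised: 31/106 − 13/86 = 0.2925 − 0.1512 = 0.1413.
- After early withdrawals, pro rata across phases: still 0.1413.
- After early withdrawals, item 6 read literally (27 and 3 before the switch): first phase 75 − 27 = 48 and 73 − 3 = 70; second phase 31 and 13 − 1 = 12. The totals are 79 and 82, as in item 20. Gap: 31/79 − 12/82 = 0.3924 − 0.1463 = 0.2461.
- The gap could also be smaller. With 12 of the 27 intervention withdrawals and 1 of the 4 control withdrawals in the second phase, it is 19/79 − 12/82 = 0.094. With 15 and 1, it is 16/79 − 12/82 = 0.056.

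**3. Bias.** If change differs by D points between phases, equally in both arms, the unadjusted contrast is biased by gap × D. D is an assumption. The values used are 5 and 10, the latter being the trial's minimum clinical difference.

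**4. Type I error.** With b = gap × D / SE, the error is Φ(−1.96 + b) + Φ(−1.96 − b).
- Month 5: SE = 20 × √(1/60 + 1/59) = 3.667.
- Month 1: SE = 20 × √(1/75 + 1/78) = 3.234, assuming the same SD.

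| Gap | D | Bias (points) | Type I error, month 5 | Type I error, month 1 |
|---|---|---|---|---|
| 0.141 | 5 | 0.71 | 5.4% | 5.6% |
| 0.141 | 10 | 1.41 | 6.7% | 7.2% |
| 0.246 | 5 | 1.23 | 6.3% | 6.7% |
| 0.246 | 10 | 2.46 | 10.3% | 11.9% |

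A simulation at month 5 (100,000 runs, SD estimated, 18/60 vs 9/59 or 24/60 vs 9/59 in the late phase) gave 5.3%, 6.3%, 6.2% and 9.6% in the same row order. With phase in the model it gave 5.0% in all four cases.

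**5. Break-even.** A month-5 type I error of 10% needs b = 0.652, that is, a bias of 0.652 × 3.667 = 2.39 points. The phases would then have to differ by 2.39/0.1413 = 16.9 points at the smaller gap, or 2.39/0.2461 = 9.7 points at the larger.

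**6. Which phase term works in the mixed model.** The expected month-5 estimate was computed by generalised least squares. It used 75 vs 78 at month 1 and 60 vs 59 at month 5, assumed within-person correlations of 0.4 and 0.7, D = 10 and no true effect.

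| Model | Pro rata split | Literal split |
|---|---|---|
| As planned | 1.38 to 1.41 | 2.45 to 2.48 |
| Phase as main effect only | 1.38 to 1.41 | 2.45 to 2.47 |
| Phase and phase-by-visit | 0.00 | 0.00 |
| Inverse-probability weights by phase | −0.02 to 0.02 | 0.00 to 0.02 |

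A main effect shifts a person's scores equally at all visits, so it leaves the contrast in change untouched.

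**7. Cost.** For arm sizes a and c, information is ac/(a + c), summed over phases once phase is in the model.
- All randomised: 47.48 / (36.99 + 9.16) = 1.029 variance inflation.
- Literal split: 40.24 / (28.47 + 8.65) = 1.084.
- Power for 10 points at 60 vs 59 (normal approximation): 77.8% unadjusted, 76.7% with inflation 1.029, 74.5% with 1.084.

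**The case against.** The strongest reply is that the harm rests on an assumed input. The documents give no phase difference in KCCQ change, and a difference in level alone cancels in the mixed model's contrast. At the as-randomised gap, a 5-point difference raises type I error only to about 5.4%, and reaching 10% takes about 17 points. This stands as a limit on size.

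The 25% figure is also open to challenge. It requires all 27 intervention withdrawals to fall among the first 75 and none among the last 31, and 27 is also the whole-trial total in Section 5, item 19. Were withdrawal risk equal in both phases, none among the 31 would have a probability of about 0.00002. On the other hand, item 6 gives 3 control withdrawals where item 19 gives 4, which suggests that item 6 may be a count at the time of the switch. The figure is therefore one reading that the text permits. Other placements of the withdrawals give gaps below 14%.

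The recorded mid-trial changes are weak evidence. Dietitian visits belong to the intervention arm, the new call was made to controls, and the revised procedure concerns retention. A change in what only one arm receives is not a phase effect common to both arms, and an additive phase term would not remove it. This also stands.

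The propensity analyses could cover phase, but phase is not named, their stated triggers are early withdrawals and baseline covariate differences, and they are supplementary. Pilot status does not remove the point either, since the plan tests superiority at two-sided 5% with a powered sample size.

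**Conclusion.** The concern holds. The allocation probability changed during the trial and the primary estimate ignores it. Of any phase difference in KCCQ change, 14.1% enters the arm contrast as randomised. The fraction is 24.6% after early withdrawals if item 6 is taken literally, and it could be below 14% if many intervention withdrawals came late.

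For assumed phase differences of 5 to 10 points, the bias is 0.7 to 2.5 points, with type I error of about 5.4% to 10% at month 5 and 5.6% to 11.9% at month 1. These figures assume SD 20 and a phase difference shared by both arms. Its size and direction are unknown, so the expected effect is modest. No bias was calculated for the utilisation outcomes, where the omission is the same in kind. The change should be made because the imbalance is built into the design and the correction is cheap. Phase adjustment does not address the separate problem of excluding 27 and 4 participants after randomisation.

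**What to change.** - Add randomisation phase (first 148 vs last 44) and phase-by-visit to the primary mixed model. The interaction is essential.
- Add phase to the ANCOVA and to the admission and emergency department models, and stratify the log-rank test by phase.
- State that the adjusted ITT and propensity analyses include phase in the same way, either as phase-by-visit or within a score used for weighting.
- In the CONSORT diagram, report numbers by phase, arm and visit, and how many early withdrawals preceded the switch. Give the date of the switch. This would settle which gap applies.

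The cost is SAP wording and a few degrees of freedom, using a variable already held. The standard error rises by about 1.4% (√1.029), or 4.1% (√1.084) at the larger gap, which is the loss of one to three points of power shown above.

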Estimates from the literature were used to calculate the sample size needed for this study for the outcomes of changes from month 0 to month 5 in our primary outcome, heart failure quality-of-life. We assumed that the standard deviations (SD) seen in the current study would be similar to that in a similar study conducted in an urban setting in the United States.¹³ Sample size calculation were based assuming 80% power for a two-sided test at alpha of 0.05, and SD of 20.0. With the outcome of change in heart failure quality of life score from baseline to 5 months, considering as a minimum clinical difference of 10 points in the heart failure quality of life score, the sample size

needed was 63 individuals in each arm. We assumed a retention in the current study of 80%, thus the sample size needed at recruitment was at least 158 (n=79 in each arm)

8) Framework

The superiority hypothesis testing framework will be used, testing whether exposure to the intervention results in better outcomes than exposure to the control standard of care. Comparisons will be presented as differences between arms in changes in outcomes from baseline to 1 month to capture changes in acute heart failure symptoms and 30-day readmission; and from baseline to 5 months of follow-up to capture longer term and potentially sustained benefits.

9) Statistical interim analyses and stopping guidance

- a. Information in interim analyses specifying what interim analyses will be carried out and listing time points
 - i. None planned
- b. Any planned adjustment of the significance level due to interim analysis
 - i. No
- c. Details of guidelines for stopping the trial early
 - i. None

10) Timing of final analyses

Final analyses will begin in Fall 2021 upon completion of all field data collection in Fall 2020 and completion of all medical record data collection (Summer 2021).

11) Timing of outcome assessments

Research staff administered full surveys to both arms at baseline, 1 month, and 5 months. Additional brief surveys were collected at months 2 and 3. Medical record data were collected continuously in both arms from 3 months prior to baseline until 9 months after baseline.

Section 4: Statistical Principles

12) Level of statistical significance

95% confidence intervals and exact p-values (or $p<0.001$) will be reported.

13) Description and rationale for any adjustment for multiplicity and, if so, detailing how the type I error is to be controlled.

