The primary outcomes were established in the protocol, and thus no adjustments will be made for multiplicity.

14) Confidence intervals

95% confidence intervals will be reported alongside exact p-values.

15) Adherence and protocol deviations

- a. Definition of exposure to the intervention and how this is assessed including extent of exposure:
 - i. Receipt of medically tailored food support AND
 - ii. Receipt of nutrition counseling and/or education
- b. Description of how adherence to the intervention will be presented.

Adherence to the intervention will be presented through a narrative summarizing the following points:

- i. % of weeks received any food support (out of weeks scheduled to receive food support)
- ii. % of food received (out of total food entitlement) (POH data)
- iii. % of food consumed (out of food received) (survey data)

iv. % of counseling or education sessions received (out of planned sessions) The cut-off points to decide if the patient is adherent to the intervention will be defined during the analysis, based on the participant's exposure to the intervention.

Definition of protocol deviations for the trial. The following protocol deviation occurred during the study and corrective actions were developed:

- a. Minor protocol deviation: Participants for study visits were seen outside of the initial protocol specified visit window (+/- 1 month). All efforts were made to reach the participants on time, but the participants were not available or were not able to be located within the window and therefore they were seen outside of the visit window. As a result, the standard operating procedure (SOP) was updated that addresses follow up and retention of participants. The SOP outlines that the research assistants will make calls and conduct home visits in case a participant misses his or her appointment date to ensure that the participants are seen with the appointment window period.

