Table 1: Baseline characteristics of CaRDS participants

Socio-demographic	Age, current gender, race/ethnicity, household size, relationship status, educational attainment
Economic welfare	Household food insecurity, sources of income, food support sources
Clinical	Heart failure quality of life; general health-related quality of life; medication inventory; blood pressure
Nutrition	Dietary quality; food consumption patterns
Mental Health	Depressive symptoms
Behavioral	Self-reported medication adherence; alcohol use, drug use
Healthcare utilization	Recent hospitalizations, ED visits, doctor visits

Section 6: Analysis

22) **Outcome definitions**

a. Aim 1: Primary Outcomes: Heart failure quality of life: The primary outcome for Aim 1 will be heart failure quality of life, which was assessed using the Kansas City Cardiomyopathy Questionnaire (KCCQ) at baseline, 1 month and 5 months, among all study participants. The Kansas City Cardiomyopathy Questionnaire is a 23-item instrument that quantifies physical function, symptoms (frequency, severity and recent change), social function, self-efficacy and knowledge, and quality of life. An overall summary score can be derived from the physical function, symptom (frequency and severity), social function and quality of life domains. A clinical summary score can be obtained from the symptom frequency and burden domains and the physical limitation domain. Scores are transformed to a range of 0-100, in which higher scores reflect better health status.

For analysis of the primary outcomes, we will compare:

- i. Change in the overall KCCQ scores from baseline to five months, by study arm.
- ii. Change in the overall KCCQ scores from baseline to one month, by study arm.
- iii. Change in the KCCQ clinical summary score from baseline to five months, by study arm,
- iv. Change in the KCCQ clinical summary score from baseline to one month, by study arm,
- v. Change in the overall physical domain KCCQ scores from baseline to five months, by study arm.
- vi. Change in the overall physical domain KCCQ scores from baseline to one month, by study arm.

b. Aim 1: Secondary outcomes:

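### Six unranked KCCQ comparisons are called primary, the sample size covers one 5-month test of an unnamed score, and pre-specification is the only reason given for not adjusting

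*Combined protocol and SAP*

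**What the plan says.** Items 4 (Objectives) and 5 (Trial design) name one primary outcome, heart failure quality of life, without a time point. Item 7 (Sample size) is based on "changes from month 0 to month 5 in our primary outcome, heart failure quality-of-life": two-sided alpha 0.05, 80% power, SD 20 and a difference of 10 points. It does not say which KCCQ score has that SD and difference.

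Item 8 (Framework) states: "The superiority hypothesis testing framework will be used". It presents the 1-month and 5-month contrasts together, gives each its own purpose (acute symptoms and early readmission; longer-term benefit), and ranks neither.

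Item 22a begins in the singular: "The primary outcome for Aim 1 will be heart failure quality of life". It then turns plural, "For analysis of the primary outcomes, we will compare", and lists six entries. The first is "Change in the overall KCCQ scores from baseline to five months, by study arm". The rest are the overall score at 1 month, and the clinical summary and physical domain scores at each of the two time points.

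Item 13, on multiplicity, says in full: "The primary outcomes were established in the protocol, and thus no adjustments will be made for multiplicity". Items 12 and 14 call for 95% confidence intervals and exact p-values.

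**The concern.** The reason in item 13 does not support its conclusion. Fixing outcomes in advance prevents picking them after the results are known. It has no effect on the chance that at least one of several true null hypotheses is rejected at 0.05. Item 13 is the place where the plan should say how type I error is controlled, and it does not.

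The primary result is also undefined. Read literally, items 13 and 22a give six primary tests, each at 0.05, while item 7 describes one. If the six results disagree, for instance a significant physical domain result at 1 month and a null overall score at 5 months, nothing in the plan says whether the primary hypothesis is supported. Nor can a reader tell whether the alpha, power and 63 per arm in item 7 apply to the result that is eventually presented as primary.

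**Working it through.** **Step 1: the plan's own sample size.** Inputs from item 7: SD 20, difference 10, two-sided alpha 0.05, power 80%, retention 80%.

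- n per arm = 2 × (1.96 + 0.8416)² × 20² / 10² = 62.8, so 63.
- 63 / 0.80 = 78.75, so 79 per arm and 158 in total.

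Both figures match item 7. They hold for one test at 0.05.

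**Step 2: upper reference for six tests.** If the six were independent, the chance of at least one false positive would be 1 − 0.95⁶ = 26.5%. This overstates the case because the scores overlap. Item 22a says of the overall score: "An overall summary score can be derived from the physical function, symptom (frequency and severity), social function and quality of life domains". Of the clinical summary it says: "A clinical summary score can be obtained from the symptom frequency and burden domains and the physical limitation domain". Physical limitation therefore enters all three scores.

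**Step 3: correlated tests.** The documents give no correlations, so these are assumed and shown as a range. Six standard normal test statistics were simulated under the null, with correlation equal to (visit correlation) × (score correlation), counting |z| > 1.96. Two ways of setting the score correlations were used.

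(a) Equal correlation between the three scores.

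(b) Scores built from their domains, with equal weights and a common inter-domain correlation r (both assumed): overall = mean of four domains, clinical summary = mean of symptom and physical, physical alone. This gives

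- overall with physical: √((1 + 3r)/4) = 0.689, 0.791, 0.880 for r = 0.3, 0.5, 0.7;
- clinical with physical: √((1 + r)/2) = 0.806, 0.866, 0.922;
- overall with clinical: the ratio of these two = 0.855, 0.913, 0.955.

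| Score structure | Visit correlation | Any of six, either direction | Any of six, favouring intervention | Three scores at 5 months only |
|---|---|---|---|---|
| (a) 0.70 | 0.3 | 20% | 10% | 11% |
| (a) 0.85 | 0.5 | 16% | 8% | 9% |
| (a) 0.95 | 0.7 | 12% | 6% | 7% |
| (b) r = 0.3 | 0.3 | 18% | 9% | 10% |
| (b) r = 0.5 | 0.5 | 16% | 8% | 9% |
| (b) r = 0.7 | 0.7 | 13% | 6.5% | 8% |

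The nominal values for one test are 5% in either direction and 2.5% in favour of the intervention.

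**Step 4: would naming one element be enough?** Fixing only the time point leaves three tests and 7–11% (last column). Fixing only the score leaves two tests, at 1 and 5 months, and 9.5%, 9.1% or 8.3% for visit correlations of 0.3, 0.5 or 0.7. Score and time point must both be named to return to 5%.

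**Step 5: is the visit correlation plausible?** The random-intercept model in the analysis methods for Aim 1, with the numbers retained in item 20 (75 and 78 at month 1; 60 and 59 at month 5, assumed to be a subset), implies a correlation of about 0.46 between the two change contrasts. This lies inside the assumed range.

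**The case against.** The strongest reply is that the error rates depend on a rule the plan does not contain. Items 12 and 14 promise estimates, intervals and exact p-values, and nothing says that one significant result out of six is a success. That is correct, and the 12–20% is therefore a conditional illustration and not the plan's error rate. The absence of a rule is itself the defect: the primary comparison is not defined.

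Second, item 5 calls this a pilot seeking feasibility and preliminary impact, and unadjusted reporting can be defended there. This limits the weight of the point. But item 13 does not rely on pilot status, and items 7 and 8 set up a powered superiority test.

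Third, the six entries can be read as one instrument at two visits, with both visits estimated from one model per score. The plan names no overall test that would join them, and item 22a heads the list with the plural.

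Fourth, the overall score at 5 months comes first in the list, and the study cited for the SD might show which score was sized. List order is not a stated hierarchy, and the cited study was not available for this check. The sponsor may well have had one score in mind; item 7 should say so.

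Finally, item 8 gives the 1-month contrast a purpose of its own, so making it secondary is partly a design preference. Keeping several primary comparisons under a stated procedure would also be coherent, at a price given under the fix.

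**Conclusion.** The concern holds. Items 7, 13 and 22a do not agree on what the primary comparison is, and the only reason given for leaving type I error uncontrolled is not a valid one. The sample size arithmetic is right, but for a single test.

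Under an any-of-six reading, the false-positive chance is 12–20% with equal score correlations and 13–18% with scores built from their domains, against 5%. In favour of the intervention it is about 6–10% against 2.5%. These figures assume that reading, the stated correlations and, for the second set, equal domain weights. The definitional gap depends on none of these assumptions. Because the trial is a pilot, this should be fixed but does not undermine the trial.

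**What to change.** Name one primary comparison in items 7, 13 and 22a, giving both score and time point. The time point should be 5 months, since that is what was sized. The KCCQ overall summary score is the natural candidate because it is listed first, but that is an inference; the sponsor should confirm which score the SD and the 10-point difference refer to. Make the other five comparisons secondary, including those at 1 month, and report them with 95% confidence intervals and no confirmatory claim. Delete the rationale in item 13. With one primary comparison no adjustment is needed, and the item can say so. Item 10 places the final analysis after field data collection ended, so add a dated statement on whether the choice was made before outcome data by arm were seen, and label it post hoc if not.

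The cost is wording and that statement. Alpha, sample size and data are unchanged. Success could no longer be claimed on a 1-month or sub-score result alone. For orientation, with SD 20 and a difference of 10, power for the single 5-month comparison is about 77% (t-test, 60 against 59) to 81% (random-intercept model using month-1 data, within-person correlation 0.3–0.7).

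Keeping six primary comparisons with Bonferroni is the costlier alternative. At alpha 0.05/6 = 0.0083, n = 2 × (2.638 + 0.8416)² × 4 = 96.9, so 97 evaluable per arm (97/0.80 = 121.25, so 122 recruited per arm). With the 60 and 59 retained, power per comparison would fall from 77.8% to 53.5% (normal approximation). Bonferroni is conservative here because the scores are correlated.
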